Patients who are identified as eligible will be screened using a survey if they are interested in participating. First, they will be asked if they sometimes drink alcoholic beverages. If yes, they will be asked how many times in the past month they have had 5 or more drinks in a day (for men) or 4 or more drinks in a day (for women). They will also be asked if, on any week in the past month, they have had more than 14 drinks (for men) or more than 7 drinks (for women). If they answer yes to either of those questions, they are considered to be an at-risk drinker and will qualify for the study. This screening may also be conducted over the phone if the participant indicates interest in the study but is unable to complete the screening procedure while visiting the clinic. If the screening procedure indicates that the participant is eligible, they may begin the study within 30 days time.

Subject Exclusion Criteria: Individuals who are HIV-negative, less than 18 years of age, who are not identified as an at-risk drinker through the alcohol screener, or who are not currently prescribed HIV medication will not be eligible to participate. For the randomized controlled trial, participants who have not had their viral load tested within the 3 months prior to beginning the intervention (3 months before baseline for the Intervention group, 3 months before the 8-week time point for the Waitlist-Control group) will not be eligible to begin the study until they have had bloodwork completed. Additionally, participants will take the AUDIT questionnaire as part of the study screener. If they score a 20 or higher, indicating alcohol dependence, they will not be eligible for study participation.

Study Recruitment

After screening, patients who are deemed eligible for the study may be recruited in the following ways:

- An IRB approved letter mailed to the patient and then after two weeks the patient may be contacted over the phone or in person at a clinic visit about the study unless they decline
- Through an approved study flyer or direct patient initiated contact to the study coordinator
- A clinic provider refers patient to study or gives patient study flyer at clinic visit

- Direct patient contact in the clinic at clinic visit
- Outreach to a patient who has previously signed an informed consent form for another research study which allowed for future contact

Study Intervention/Investigational Product

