2. Upon arrival to the clinic for the first intervention session, the patients will be shown to a private room to begin their first videoconferencing session
3. The patient will be given a laptop to complete the initial assessment battery
4. If the participant is in need of a study phone, the VA coordinator will provide this phone, along with the breathalyzer, to the participant
5. Participants will begin the first intervention session, which will consist of the following content/tasks:
 - a. Introductions and orientation to the technology (smartphone and breathalyzer, stored at the clinic; tutorial handouts provided)
 - b. Review of self-monitoring procedures and setting of "do not disturb" hours
 - c. Review of breathing awareness exercise
 - d. Scheduling follow-up intervention sessions for weeks 2-8, conducted via mobile phone
 - e. A short post-session satisfaction survey, delivered via text message and completed immediately following the session.
6. The day after the first session, participants will begin self-monitoring their alcohol, medication use, and mental health
 - a. They will be texted at two random times each day using an automated software to complete a breathalyzer reading and finish a survey
 - b. If participants do not respond to the request within 30 minutes, a text reminder will be sent, followed by another an hour later.
 - i. If the participant is in a situation where they are unable to complete the breathalyzer test, they will be able to respond to the text message and request a follow-up reminder two hours later.
 - c. If participants wish to go to sleep for the night and have not yet received their evening reminder, they can elect to complete a breathalyzer reading and survey before going to bed.
 - d. Self-monitoring will continue through the end of week 8 (until they return to the VA to complete their post-test and return their equipment)
 - e. Participants will be instructed to call the interventionist if they have any technical difficulties throughout the course of the study
7. Sessions 2-8 of the intervention will be conducted via phone call, with patients instructed to find a private room at home from which to speak with their counselor.
 - a. After each session, the participant will complete a short post-session satisfaction survey, delivered via text message and completed immediately following the session

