 - i. If patients cannot be reached, researchers will attempt to contact them three additional times (one day later, three days later, and one week later). If they cannot be contacted by the third attempt, they will be considered lost to follow-up and will not be contacted again.
13. After the participant completes the study, a retrospective chart review will be conducted to obtain viral load measurements (minimum of 2) from the participant during the time period beginning 3 months prior to their entry into the study and up to 6 months after their entry into the study.

3b. Waitlist-control group

1. After randomization and enrollment, the participant will complete the baseline assessment either at the time of enrollment, at home, or during a subsequent appointment within the next 30 days
2. The interventionist will call the participant after enrollment and do the following:
 - a. Introduce themselves to the patient
 - b. Describe the study timeline
 - c. Discuss follow-up contact times and encourage the participant to stay in contact
 - d. Remind participant of incentives they will receive for participating
 - e. Provide information about the baseline assessment (if the participant has not already completed it)
3. The interventionist will contact participants using their chosen method of communication after 4 weeks to maintain contact and ensure that no adverse events have occurred
4. At 7 weeks, the interventionist will contact participants to obtain their availability for the next week to schedule the first intervention content session based on the shared calendar
5. One day before the videoconferencing session, the researcher will contact the participant via the participant's chosen method of contact to remind them of their appointment
6. At 8 weeks, the patient will come into the clinic to begin the intervention.
7. The patient will be given a laptop to complete the initial assessment battery
8. If the participant is in need of a study phone, the VA coordinator will provide this phone, along with the breathalyzer, to the participant
9. The participant will begin the first intervention session, which will consist of the following content/tasks:
 - a. Introductions and orientation to the technology (smartphone and breathalyzer, stored at the clinic; tutorial handouts provided)

- b. Review of self-monitoring procedures and setting of “do not disturb” hours
 - c. Review of breathing awareness exercise

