- After Session 5: \$20 for phone session, up to \$15 for daily monitoring
- After Session 6: \$20 for phone session, up to \$15 for daily monitoring
- After Session 7: \$20 for phone session, up to \$15 for daily monitoring
- After Session 8: \$20 for phone session, plus up to \$15 for daily monitoring

- After Week 16 visit to the VA: \$40 for questionnaire, plus up to \$15 for daily monitoring
- After Week 20 Booster Session: \$20
- After Week 24 questionnaire: \$40

Study Schedule

Participants in the waitlist-controlled trial will be enrolled in the study for a total of 24 weeks (168 days), whether they are in the intervention or waitlist-control group. They will participate in eight intervention sessions and one booster session. The first and last sessions will take 1.5-2 hours, depending on how long the participants take to complete the surveys. Sessions 2-8 and the booster session will take 30 minutes each. After each intervention session, they will complete a short 5-minute questionnaire on their mobile phones. During the intervention, they will also complete two daily assessments, which will take approximately 20 minutes total. Each participant will also complete two additional assessment batteries, which will take 45-60 minutes. Thus, the total time commitment is approximately 27-28 hours. On the rare occasion when study visits may be unexpectedly delayed, visits will not be delayed more than 1 week. See the following flowchart for detailed information about the participant timeline.

Patient Compensation

Participants will receive the following:

- \$20 for attending all intervention sessions via videoconferencing or phone (including booster session – 9 sessions)
- \$1 for each completed breathalyzer reading (up to 14/week, with \$1 bonus for completing all readings)
- \$30, \$40, \$40, and \$40 for completing health questionnaires
- TOTAL POSSIBLE: \$450

5. Data

Collection and record keeping

Both intervention and waitlist-control groups will complete an extensive assessment battery at baseline, 8 weeks, 16 weeks, and 24 weeks. They will also complete daily monitoring of alcohol and medication use during their 8-week intervention period. The following outcome variables will be explored via the listed methods of data collection:

Confidential online questionnaires, completed on tablets or mobile phones at baseline, and 8-, 16-, and 24 week follow-ups, concerning the following variables:

- Post-Traumatic Stress Disorder Symptoms

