In the event that identifying information is released to an unauthorized party, the serostatus of participants could be revealed to unwanted individuals. This could potentially cause harm, but is unlikely considering the careful plans in place regarding data management and protection. All possible measures will be taken to protect information provided through surveys, interviews, and intervention participation, and confidentiality will be respected. Following completion of data collection, responses will become anonymous as identifying information is permanently deleted. For these reasons, we estimate that this minimally-invasive project poses minimal risk.

STATISTICAL ANALYSIS PLAN

For the randomized controlled trial, data analytic methods will be focused on examining acceptability and feasibility, as well as effects on alcohol intake, HAART adherence, and HIV-related medical outcomes (CD4 count and viral load). Intervention adherence, daily monitoring adherence, and session acceptability will be described using descriptive statistics. Session attitudes will be assessed using several 5-point semantic differential attitudinal measures rating the session, including Boring/Interesting, Unpleasant/Pleasant, Bad/Good, Useless/Useful, and Negative/Positive. Scores on the session attitude semantic differential measures will be reverse-coded where required and averaged to form an overall attitude score, with “0” being “neutral.”

We will provide descriptive summaries for the outcome variables, including mean, median, and standard deviation for continuous variables and counts and percentages for categorical variables. We will summarize the outcome variables overall and across the intervention groups. In assessing the differences in alcohol use and medication adherence between the two groups during the 8-week intervention period, we will utilize the Kruskal–Walli’s test, a non-parametric statistical approach, to compare the distribution of outcome variables. The general linear model (ANOVA) will be used to estimate the difference between alcohol use and medication adherence among the groups, and the estimation of the effect size (Cohen’s D) at the end of the 8-week intervention period. While this study was not powered to detect significant differences, the goal of these analyses is to observe changes and effect sizes that may provide preliminary evidence of efficacy.

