To examine intervention effects as assessed through daily surveys, we will examine responses to the morning survey question asking if participants had consumed alcohol on the previous day (yes/no), whether or not they reported a positive breathalyzer reading (> 0.0), and if they had taken all of their HAART on the previous day (yes/no). Within the 8-week intervention period and using the daily data, we will assess the change in the proportion of participant's alcohol use, the proportion of positive breathalyzer readings, and the proportion of their medication use from the beginning of week 1 to the end of week 8 using McNemar's matched pair test. This test will allow us to address the interdependency in the repeated measurements. We will account for missing survey responses by considering two scenarios: First, assuming they were missing completely at random and remained missing, and second, that missing values were indicative of alcohol use/medication nonadherence and were thus filled in as drinking days/positive breathalyzers/nonadherent days (a conservative approach).

All participants will have received the intervention by the end of the 8 week (2-month) post-intervention period. To examine long-term intervention effects, participants from both the waitlist-control and intervention group will be combined into a single dataset. A generalized linear model (via SAS GENMOD PROCEDURE) and a multiple linear regression model will be fit to the change from baseline for each outcome measure. Change from baseline is the difference between the baseline value and values obtained at subsequent time points: 8 weeks (immediate post-intervention; T2 for intervention group and T3 for waitlist-control), and 16 weeks (2 months post-intervention; T3 for intervention group and T4 for waitlist-control) for each outcome measure. The rationale for fitting the change from baseline is that this model removes the effect of baseline differences that may exist from the model. All statistical hypothesis tests will be conducted using the standard 5% significance level. SAS Version 9.4 (TS1M1, SAS Institute, Cary, NC), will be used for all analyses.

References

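### The SAP presents an uncontrolled week-1 to week-8 change in the daily data as intervention effects; it should be labelled as descriptive within-person change

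*Combined protocol and SAP*

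**What the plan says.** The third paragraph of the Statistical Analysis Plan opens with "To examine intervention effects as assessed through daily surveys". It names three daily yes/no outcomes: any drinking on the previous day, a positive breathalyzer reading, and all HAART taken on the previous day. Change in each is tested with McNemar's matched-pair test "from the beginning of week 1 to the end of week 8". There is no group term, and the SAP applies the 5% level to all its hypothesis tests.

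The timing of the daily data is set elsewhere:

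- Section 5 (Data, Collection and record keeping), for both groups: "They will also complete daily monitoring of alcohol and medication use during their 8-week intervention period".
- Step 3a item 6 (intervention group) and Step 3b item 10 (waitlist group), in the same words: "The day after the first session, participants will begin self-monitoring their alcohol, medication use, and mental health".
- Step 3b item 6 (waitlist group): "At 8 weeks, the patient will come into the clinic to begin the intervention". The breathalyzer is handed over at that visit.

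The second paragraph of the SAP plans a separate comparison of the two randomised groups over the first eight weeks (Kruskal–Wallis, ANOVA, Cohen's d). It says that the study was not powered and that the aim is to "observe changes and effect sizes that may provide preliminary evidence of efficacy".

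**The concern.** An intervention effect is a contrast with what would have happened without the intervention. The daily data contain no untreated person-week. The waitlist group has no daily data during its control weeks, and neither group has any before Session 1. The test therefore shows whether the proportion changed over eight weeks, not why.

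Several other explanations follow from the design. Screening asks "how many times in the past month they have had 5 or more drinks in a day" (the threshold for men) or about a heavy week in the past month, and a participant may start within 30 days. Regression to the mean is therefore plausible, most of all in the group treated at once. The protocol provides for a COVID-19 period, when drinking may change for outside reasons. Reporting may also change over eight weeks of twice-daily prompts whose results are discussed with the counselor.

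At stake is what a report may conclude. Nothing in the SAP limits this analysis to description, so a significant result could be reported under the SAP's own label as an effect of TRAC.

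**Working it through.** **Step 1: is there any control for the daily data?**

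| Study weeks | Intervention group | Waitlist group |
|---|---|---|
| Before Session 1 | no daily data | no daily data |
| 0–8 | daily data, on TRAC | no daily data |
| 8–16 | monitoring ended | daily data, on TRAC |

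No row holds treated and untreated daily data together, and no group has daily data both before and during TRAC.

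**Step 2: how often would drift alone give a significant result?** The plan states no figure to reproduce.

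From the documents: recruitment goal 50; 5% level. Assumed, because the documents give no value: two-sided test; one binary pair per participant; all 50 pairs complete; week-1 proportion p1 = 0.40; latent (bivariate normal) correlation 0.4; no intervention effect; drift of 0, 5 or 10 points downward, so p2 = 0.40, 0.35 or 0.30.

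- Both days positive: p11 = Φ₂(z(p1), z(p2); 0.4).
- Discordant cells: π10 = p1 − p11 and π01 = p2 − p11.
- Number of discordant pairs: D ~ Binomial(50, π10 + π01). Given D, the improving pairs are b ~ Binomial(D, π10/(π10 + π01)), and c = D − b.
- Asymptotic test rejects if (b − c)²/(b + c) > 3.84. Exact test rejects if 2·P(Bin(D, 0.5) ≤ min(b, c)) < 0.05.
- The rejection probability is the sum over all D and b.

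| Drift | p11 | π10 | π01 | Asymptotic | Exact |
|---|---|---|---|---|---|
| 0 | 0.222 | 0.178 | 0.178 | 5.1% | 2.9% |
| 5 points | 0.200 | 0.200 | 0.150 | 9.2% | 5.8% |
| 10 points | 0.176 | 0.224 | 0.124 | 22.4% | 16.1% |

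**Step 3: sensitivity.**

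- Starts of 40–60% and latent correlations of 0.2–0.6, N = 50: a 5-point drift gives 8.7–9.5% (5.3–6.1% exact); a 10-point drift gives 19–25% (13–19% exact).
- 40 complete pairs (assumed), other inputs as in Step 2: 7.7% and 17.7% (4.8% and about 12% exact).
- Direction: with a 10-point downward drift nearly all rejections point to improvement. With a 10-point upward drift from 40%, the test rejects 21.5% of the time, nearly always towards worsening.

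**Step 4: what a control would do.** If two groups of 25 (1:1 assumed) drift equally to a common week-8 proportion between 0.30 and 0.50, a between-group test rejects 5.4–6.5% of the time (pooled z) or 2.3–3.3% (Fisher). Shared drift cancels. The daily data cannot supply this comparison, because the waitlist group has none in weeks 0–8.

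**The case against.** The strongest reply is that this is a declared, unpowered pilot whose efficacy language belongs to another analysis. That largely stands. A reader might infer that the SAP commits itself to citing the McNemar result as efficacy. It does not: the sentence about preliminary evidence closes the between-group paragraph, before the daily analysis is introduced. What remains is the separate label on the daily analysis. Low power does not answer that, since the problem is attribution and not missed effects.

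Three further inferences are tempting and not supported.

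- *Starting after Session 1 inflates the apparent benefit.* If anything it does the reverse: an effect already present in week 1 would make the later change understate benefit. Session 1 is also mostly introduction and phone training, with the change plan left to Session 2. The argument rests on the missing control.
- *Reactivity to self-monitoring is a bias.* The protocol describes TRAC as a behavioral skills and self-monitoring intervention, so reactivity is part of the package effect.
- *The waitlist group's questionnaire change from baseline to week 8 could serve as the drift estimate.* It uses a different instrument, in people without daily prompts or counselor review. The battery listed in section 5 names neither medication adherence nor breathalyzer readings, so two of the three daily outcomes would have no counterpart.

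The plan does have partial safeguards. Filling missing responses as drinking, positive or nonadherent days guards against fatigue that shows as non-response, and would push towards apparent worsening if gaps grow over time. Breathalyzer readings prompted at random times limit simple misreporting. Neither replaces a control.

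**Conclusion.** The point holds as one of labelling and inference. The daily analysis is an uncontrolled within-person comparison, and the SAP presents it as examining intervention effects. It cannot separate TRAC from regression to the mean, calendar or COVID-period change, or altered reporting, in either direction.

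The size is illustrative. Under the assumed 40% start, latent correlation 0.4 and 50 complete pairs, drift alone gives rejection rates of about 9% (5 points) and 22% (10 points), or 6% and 16% with the exact test. A small drift with the exact test thus stays close to nominal; a moderate one does not. The documents do not show how large any drift would be, or that it would favour TRAC.

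The randomised week-8 comparison is unaffected, so the severity is minor.

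**What to change.** In the daily-data paragraph of the SAP, replace "To examine intervention effects as assessed through daily surveys" with wording such as *To describe within-person change during the intervention period (uncontrolled)*. Add two statements: that this analysis does not by itself support an intervention effect, and that statements of preliminary efficacy rest on the randomised between-group comparison at week 8 in the preceding paragraph. Carry the same label into tables and the report.

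The McNemar test and both missing-data scenarios can stay as they are. No new data, visits or participants are needed. The cost is a few sentences and a less favourable claim from the daily data, most plainly for the breathalyzer readings, which have no between-group counterpart.

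### The McNemar pair for the daily outcomes is undefined; comparing each participant's week-1 and week-8 proportions, with a 95% CI, is a cheap improvement

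*Combined protocol and SAP*

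**What the plan says.** The daily-survey paragraph of the Statistical Analysis Plan takes three outcomes: the answer to "the morning survey question asking if participants had consumed alcohol on the previous day", "whether or not they reported a positive breathalyzer reading", and whether all HAART was taken on the previous day. Change is assessed "from the beginning of week 1 to the end of week 8 using McNemar's matched pair test". The reason given is: "This test will allow us to address the interdependency in the repeated measurements". The same paragraph also describes the breathalyzer outcome as "the proportion of positive breathalyzer readings". Missing responses are handled in two ways: left missing, or filled in as drinking, positive or nonadherent.

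The protocol (section 4, Step 3a, item 6) sets the data flow: "The day after the first session, participants will begin self-monitoring their alcohol, medication use, and mental health"; "They will be texted at two random times each day using an automated software to complete a breathalyzer reading and finish a survey"; and, for the intervention group, "Self-monitoring will continue through the end of week 8". For the waitlist group, Step 3b item 10d ends monitoring on the day of the final intervention session. The Control Group payment list (Step 5) still includes monitoring money after the Week 16 visit. Section 5 (Collection and record keeping) describes monitoring over an 8-week intervention period.

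The SAP promises counts and percentages for categorical outcomes. It names no confidence interval for the daily outcomes.

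**The concern.** McNemar's test needs one binary pair from each independent unit. The SAP leaves open which day supplies each half of the pair, whether the unit is the participant or the person-day, and how two breathalyzer readings a day become one value. Two competent analysts could therefore report different changes from the same data.

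Each obvious reading has a weakness. First against last day discards nearly all the monitoring and depends on two single days. Pooling day pairs uses more data but treats several pairs from one participant as independent. At stake are the precision and reproducibility of a pilot estimate that may inform later work.

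**Working it through.** **Inputs from the documents.** N=50 (Study Objectives; Step 1); 8 weeks of monitoring; two readings a day, 14 a week (Patient Compensation); 5% significance level, taken as two-sided. The plan gives no power or precision figure for this analysis, so there is none to reproduce.

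**Assumed inputs.** Drinking days fall from 40% to 28%, linearly on the logit scale from day 1 to day 56. Random intercept SD is 1.2, random slope SD 0 to 1.5, and 20% of days are missing at random. The documents give none of these.

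**1. Data used.** 8 × 7 = 56 days. First against last day uses 2/56 = 3.6%; week 1 against week 8 uses 14/56 = 25%.

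**2. Complete first/last pairs when missing values stay missing.** N × (1 − m)². At m = 20%: 50 × 0.8² = 32. At 10% and 40% missing: 40.5 and 18.

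**3. Half-width by hand.** t × SD/√n, with SDs implied by the assumed model at little or no slope variation.
- First v last day, SD about 0.59: 2.04 × 0.59/√32 = 0.21, or 21 points.
- Weekly proportions, SD about 0.26: 2.01 × 0.26/√50 = 0.07, or 7 points.

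**4. Simulated half-widths (percentage points).**

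| Scenario (assumed) | First v last day | Week 8 − week 1 |
|---|---|---|
| 20% of days missing, left missing | about 21 | 7-9 |
| Same, with serial correlation | not compared | 8-10 |
| 20% of days missing, filled in as drinking | 19 | 7-8 |
| 20% of people stop in weeks 2-7, filled in | 18-19 | 10-11.5 |

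Stronger serial correlation (latent SD 2, rho 0.8) widened the weekly figure to 10.6-11.1. A different set of assumptions (50% to 35%, intercept SD 1.5, no missing days) gave 16-17 against 6-8.

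**5. Type I error at nominal 5%.** First v last day: about 2-6%, depending on the exact or chi-square version and the missing-data scenario. Weekly paired t: 4-6%. Pooled day pairs: 5.1, 5.7, 8.3 and 10.2% at slope SD 0, 0.5, 1.0 and 1.5. With serially correlated days (latent SD 1, rho 0.7), pooled pairs gave 7.6% even at slope SD 0, and 10.5% at slope SD 1.0. Stable differences between people do not inflate the error; differing trends do, and so does serial correlation.

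**6. Change of estimand.** Week 1 centres on day 4 and week 8 on day 53, so the expected weekly fall is about 12 × (53 − 4)/(56 − 1) = 10.7 points, against 12 for first v last day. If the fall is complete by about day 17, it is about 10.

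**7. Dropout with fill-in.** If 20% have stopped before week 8 and no other days are missing, the last-day value is 0.8 × 28 + 20 = 42.4%, against 40% at the start: +2.4 points. The weekly means are about 39.3% and 28.7%. Filled in, week 8 is 0.8 × 28.7 + 20 = 43.0%, a change of about +3.6. Simulation gave about +2 and +3.5. A true fall appears as a rise under either method.

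**8. Breathalyzer unit.** If 10% of readings are positive, positive days range from 10% (the two readings always agree) to 1 − 0.9² = 19% (independent).

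**9. Week 8 in the waitlist group.** The payment list has 7 monitoring blocks (after Sessions 2-8) plus 1 (after the Week 16 visit): 8 × 7 = 56 days. If monitoring stopped at Session 8, there would be 7 × 7 = 49 days and no week 8.

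**The case against.** **A reader might infer that the planned test is invalid.** The documents do not support that. With one pair per participant McNemar's test is sound, and the SAP's sentence about interdependency is correct. Nothing says pooling is intended. But nothing says one pair per person either, and the references to daily data and to readings could fit pooling, so the ambiguity stands.

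**A reader might infer that the plan itself makes precision the goal here.** The SAP's sentence about changes and effect sizes closes its paragraph on the between-group comparisons; applying it to the daily data is inference. Percentages are already promised, so only the interval is missing.

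**A reader might infer that the first day biases the result.** Monitoring starts the day after Session 1 and the morning question looks back a day, so the first drinking and HAART answers describe the Session 1 day. That day is normally a clinic visit, but the documents give no ground for a size or direction of effect. The breathalyzer outcome is untouched, and under the COVID-19 provision Session 1 is remote. What remains is that any single day is a fragile anchor.

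**The size of the gain is conditional.** It shrinks to about 1.6-1.9-fold under dropout with fill-in (18/11.5 and 19/10). It also applies only to the first v last day reading.

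**The choice of main analysis is partly preference.** Weekly proportions still use only a quarter of the days. A GEE linear trend over all days had higher simulated power under steady change (96/94/85/73% against 83/80/72/63% at slope SD 0/0.5/1.0/1.5), but lower if the fall is early (58% against 63% at slope SD 1.0). The weekly difference stays closer to the SAP's stated contrast and does not assume a linear course.

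**Conclusion.** The point holds as a cheap improvement. The pair and the breathalyzer unit are undefined. The valid one-pair reading uses 3.6% of the monitored days, and the pooled reading can raise type I error to about 8-11%. Weekly proportions cut the CI half-width from about 21 points to 7-9 (8-10 with serial correlation), or from about 18-19 to 10-11.5 with 20% dropout and fill-in.

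The missing definitions are certain from the text. The direction of the precision gain held in every scenario compared, but its size rests on assumed rates, missingness and correlation. No method here rescues the fill-in scenario from reversing the sign under dropout.

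**What to change.** In the SAP's daily-survey paragraph:

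- **Main analysis.** For each participant, compute the proportion of answered days that are yes in week 8 minus that in week 1. Report the mean difference with a 95% CI (paired t) for drinking days, positive breathalyzer and all HAART taken.
- **Unit.** State whether the breathalyzer outcome counts days or readings.
- **Missing data.** Run both existing scenarios, and report how many participants stopped monitoring before week 8.
- **Interpretation.** Describe the result as within-intervention change, because neither group is monitored daily outside its intervention period.
- **Secondary, if wanted.** A logistic GEE trend over all days, clustered on participant, with a small-sample correction to the standard error.
- **If McNemar is kept.** State one pair per participant and the exact days.
- **Week 8.** Reconcile the end-of-monitoring wording in Steps 3a and 3b with the Control Group payment list and section 5, so that week 8 is defined for the waitlist group.

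The cost is SAP wording and a few lines of SAS, with no new data. Downsides: the estimand becomes a weekly average, so the expected change is smaller (about 10.7 or 10 points rather than 12 in the example). Each participant counts equally however many days were answered. When missing values stay missing, a participant needs at least one answered day in both weeks. The t interval is approximate if positive breathalyzers are rare, although simulated type I error was 4-5% at 2-5% positive.
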